Title: Utility of Restrata With Split Thickness Skin Graft to Reconstruct the Forearm Donor Site

NCT Number: NCT04829331

ID: 21-RES-003

Document Date: 22 APRIL 2021

Title:

Utility of Restra (Acera Surgical Inc., St. Louis, MO) in forearm flap reconstruction with donor site healing and function.

Objective:

Understand association between use of Restra (Acera Surgical Inc., St. Louis, MO) in forearm flap reconstruction with donor site healing and function.

Hypothesis:

Use of Restra in combination with split-thickness skin graft for reconstruction of forearm flap reconstruction donor site will be associated with decreased occurrence of tendon exposure at four weeks post-operatively when compared to split-thickness skin graft alone.

Design:

Randomized controlled trial.

Setting:

Single institution, Nebraska Methodist Medical Center

Population:

Adult patients undergoing radial forearm free flap or ulnar forearm free flap at a single institution.

Intervention:

Reconstruction of forearm harvest site using Restra with a split-thickness skin graft.

Control:

Reconstruction of forearm harvest site using split-thickness skin graft alone.

Inclusion Criteria:

1. All patients age 19 or greater that will undergo radial forearm free flap or ulnar free flap.
2. Photo documentation of wound bed at two weeks and four weeks must be obtainable either by physician or patient.

Exclusion Criteria:

1. Active systemic immunosuppression (active use of high-dose steroids ($\geq 40\text{mg}$ prednisone daily or equivalent) or other immunosuppressive medications OR medical conditions causing immunosuppression, i.e. human immunodeficiency virus etc).
2. Diabetes mellitus with most recent Hemoglobin A1c ≥ 10.0 within 30 days prior to surgery.
3. Morbid obesity (BMI >40).
4. Inability to maintain wrist immobilization for full planned period.
5. Severe malnutrition (prealbumin levels <10 mg per dL within 30 days prior to surgery OR BMI <15 (very severely underweight)).
6. Other conditions felt to significantly impair wound healing per surgeon discretion.

Primary Outcomes:

1. Tendon exposure at four weeks post-operatively (Yes/No).

2. Percentage of surface area of split-thickness skin graft incorporation at four weeks post-operatively.

Secondary Outcomes:

1. Tendon exposure at two weeks post-operatively (Yes/No).
2. Percentage of surface area of split-thickness skin graft incorporation at two weeks post-operatively.

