3. Aesthetic appearance of donor site per surgeon rating (graded 1-10).
4. In patients with tendon exposure, time to complete wound epithelialization (measured as time from surgery to first documentation of complete epithelialization in days).
5. Need for re-operation on forearm or secondary wound care strategy after tendon exposure.
6. Forearm infection requiring surgical drainage and/or antibiotics.

Goal Enrollment:

40 total patients with 1:1 group enrollment. Power analysis was performed to identify necessary sample size to detect an absolute reduction of tendon exposure at four weeks of 15% (25% baseline, 10% expected rate with intervention with power of 80% and alpha 0.05). Under these assumptions, 100 patients would need to be recruited into each arm. Recent historical review of institutional volume demonstrates a rate of approximately 35 forearm flaps annually (2019-2020 data). Assuming a 70% study enrollment rate, we would meet enrollment goals in approximately eight years. This time commitment is felt by the study authors to exceed what is reasonable without first generating preliminary data. The proposed sample size is therefore practically derived based annual surgical volume at this institution and available resources from our industry partner. We recognize the limitations in this study, therefore, and that this design is not truly hypothesis testing. Using the above assumptions, we expect goal enrollment to be met within approximately 18 months.

Covariates Recorded:

1. Demographic data - Age, sex, race, ethnicity, BMI.
3. Medical history - Modified frailty index - 5, diabetes mellitus, coronary artery disease, peripheral artery disease, immunosuppression.
4. Social history - Smoking status (current/former/never, total py), alcohol use pattern
5. Wound surface area in square cm.

Randomization:

Occurs when the patient is scheduled for surgery. A simple randomization strategy will be utilized by creating a randomization list using <https://www.graphpad.com/quickcalcs/randomize1/>, which will ensure equal group distribution. The surgery scheduler will assign patients to their category based on this pre-determined list in consecutive order based on date of surgery scheduling request rather than surgical date to minimize risk of bias.

Consent:

Written informed consent will be obtained at the time of study enrollment and will be stored securely by the Methodist research office. This form is separately attached.

Protocol:

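### The randomization procedure does not conceal allocation: nothing hides upcoming list entries or requires eligibility and consent to be recorded before an entry is read

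*Protocol*

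**What the plan says.** The Protocol's Randomization section sets out the procedure.

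- Timing: "Occurs when the patient is scheduled for surgery".
- Source: "A simple randomization strategy will be utilized by creating a randomization list using" a public web tool, "which will ensure equal group distribution".
- Use of the list: "The surgery scheduler will assign patients to their category based on this pre-determined list in consecutive order based on date of surgery scheduling request", and this is done "rather than surgical date to minimize risk of bias". No other safeguard is stated for allocation.

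The Consent section adds: "Written informed consent will be obtained at the time of study enrollment". It says that the consent "will be stored securely by the Methodist research office". It does not say whether enrolment comes before or after the assignment is read.

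Exclusion criterion 6 reads: "Other conditions felt to significantly impair wound healing per surgeon discretion".

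The blinding in item 15 of the Protocol's numbered procedure applies to the two independent surgeons who rate photographs. Item 16 provides for descriptive statistics and univariate comparisons between groups.

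**The concern.** Random assignment protects the comparison only if those who decide on a patient's entry do not know the next arm. Here the sequence exists in advance and is read off in order. The Protocol mentions no sealed envelopes, no release by a third party, no limit on who may see the list, and no rule that eligibility and consent are settled first.

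The Protocol also leaves room to act on such knowledge. A patient may be approached or not, a scheduling request may be timed, and criterion 6 allows exclusion on judgement for the very property, wound healing, that drives the primary outcomes. If higher-risk wounds were steered towards or away from the matrix arm, the estimated effect would be biased, and enrolling more patients would not remove that bias.

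This is not a matter for a statistical analysis plan. Custody of the list and release of assignments are trial conduct, and the Protocol prescribes a procedure for them.

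**Working it through.** **The plan's own figure.** The only computed sample size is 100 per arm for 25% versus 10%, power 80%, alpha 0.05. It reproduces exactly with a two-sided, pooled-variance formula without continuity correction. The present point does not depend on it.

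**What the stated safeguard covers.**

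- Reordering by operation date: prevented by the request-date rule.
- Foreknowledge of the next entry: not addressed.
- Exclusion or non-approach after the next arm is known: not addressed, because neither section fixes the order of eligibility, consent and assignment.
- Two requests on one date: no order defined.

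**How predictable the sequence is.** Inputs: 40 patients, 1:1, list balanced at 20/20 (Goal Enrollment; Randomization).

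- Someone who sees the list foresees 40 of 40 assignments.
- Someone who sees only past assignments and guesses the arm with more places left expects n + (4^n / C(2n,n) − 1)/2 correct guesses. With n = 20 this is 20 + (7.98 − 1)/2 = 23.5 of 40 (59%), against 20 by chance.

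Visibility of the list is therefore the main route.

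**Room for selection.** Volume is about 35 flaps a year and enrolment 70% (Goal Enrollment), so 35 × 0.70 = 24.5 patients a year and 40/24.5 = 1.63 years. In that time 35 × 1.63 = 57 flaps are expected, so about 17 patients stay out. A few selective omissions would not stand out among them.

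**Illustration of size.** Assumed, not in the Protocol: 20% of patients are high risk with 50% tendon exposure, and the rest have 19%. Overall: 0.20 × 0.50 + 0.80 × 0.19 = 0.252, close to the Protocol's 25% baseline. Exchanging k high-risk for k low-risk patients between arms of 20 moves the expected difference by 2 × k × (0.50 − 0.19)/20.

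- k = 1: 2 × 0.31/20 = 3.1 points.
- k = 2: 4 × 0.31/20 = 6.2 points.
- If the matrix cuts every risk by the hoped-for ratio 10/25 = 0.4, the shift is k × 0.31 × (1 + 0.4)/20: 2.2 points for k = 1 and 4.3 for k = 2.
- Removing one high-risk patient from one arm, with a low-risk patient in that place, moves that arm by 0.31/20 = 1.55 points, half of one exchange.

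All these shifts are proportional to the assumed risk gap: half the gap gives half the shift.

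**Same-day requests.** Assume 250 working days a year: 1.63 × 250 = 408 days. Expected same-day pairs: (40 × 39/2)/408 = 780/408 = 1.91. Order matters only if the two adjacent entries differ in arm, which on a 20/20 list has probability 20/39 = 0.51. That leaves 1.91 × 0.51 = about 1.0 pair in the whole trial.

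**The case against.** The strongest objection is that the text does not say what a critical reader may take from it. One might infer that the scheduler holds the whole list, that the surgeons can see it, or that patients are always assigned before the trial is offered. None of this is written. The Protocol says only that the scheduler assigns from the list in consecutive order. The supported statement is that concealment is not described, so foreknowledge is possible. That it occurs is not shown.

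There are also partial safeguards. A scheduler assigns, not the enrolling surgeon, and the order follows a rule chosen to limit bias. Both narrow the routes to manipulation, but neither hides the next entry. The blinded photo raters protect outcome assessment only.

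The illustration rests on one assumed scenario. With 8 high-risk patients among 40, or 4 per arm, two exchanges make it 6 against 2, which is severe. Non-approach and exclusion remove patients and do not swap them, so they move the difference less per patient. Exclusion criteria 1 to 5 already remove several severe healing risks. Even 6.2 points is about half the standard error of the difference at 20 per arm: √((0.25 × 0.75 + 0.10 × 0.90)/20) = 11.8 points.

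A reader might also infer that such bias could be neither detected nor corrected. That goes too far. Frailty index, diabetes, peripheral artery disease, smoking, BMI and wound area are recorded, and gross imbalance in them would show. But 20 per arm gives little power to see it, the surgeon's judgement is not a recorded covariate, and the stated comparison is univariate.

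Finally, the Protocol calls the trial preliminary and not truly hypothesis testing. This limits the weight of any one estimate. It does not excuse the gap, since a biased preliminary estimate would mislead the planning of a larger trial.

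**Conclusion.** The point holds as a weakness of the prescribed procedure. A pre-made list is read consecutively at scheduling, without concealment and without prior recording of eligibility and consent, and the one stated safeguard does not address foreknowledge. That anyone can see the list in advance is an inference from the plain reading, because the Protocol is silent on access.

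The possible size is a shift of about 3 to 6 points for one or two exchanged patients, against a hoped-for difference of 15. It rests on assumed risks of 50% and 19%, equal in both arms; it falls to about 2 to 4 points if the matrix works as hoped, and scales with the risk gap. Same-day ordering adds about one consequential pair and is a side issue. The matter should be corrected, because the remedy is cheap and later analysis can repair little of the damage.

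**What to change.** Amend the Randomization section as follows:

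- The Methodist research office, or another person outside scheduling and enrolment, holds the list.
- That holder releases one assignment at a time to the scheduler, only after eligibility (including a recorded decision on criterion 6) and written consent are logged.
- Assignments follow the logged date and time. This replaces the request-date rule and also settles same-day requests.
- Later entries are not visible to the scheduler or the surgeons.

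The Consent section should state the matching order: consent first, then assignment.

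The cost is a short amendment and, at 24.5/12 = 2.0 patients a month, about two messages a month. The Protocol gives the research office only the storage of consents, so its agreement to the new task must be obtained. Two exclusion criteria use laboratory values from the 30 days before surgery. For patients booked further ahead, release may therefore come after scheduling, and the sentence on the timing of randomization should allow for that. Sample size and treatment do not change.

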13. If at any point the treating physician feels that the primary treatment strategy is inadequate or inappropriate, a secondary wound care strategy (alternative treatment, negative pressure therapy, surgical debridement, repeat grafting, etc) may be pursued.
14. In any case of incomplete graft incorporation and/or tendon exposure, further photo documentation will be obtained by the patient, family, or home health or wound team, or physician until epithelialization is complete and further wound care is no longer needed. Details of continued follow-up visits and methods of further documentation will be individualized so as to minimize excessive demands on patient resources.
15. Photos of donor sites at each time period will be submitted for evaluation by two independent surgeons who possess expertise in evaluation of free flap donor site wounds and skin grafts but who will not be involved in enrollment of patients in this trial or of management of their wounds. The percentage of graft incorporation and presence or absence of tendon exposure will be documented by each physician in a blinded fashion. The independent surgeons will also rate donor site graft aesthetic appearance on a 1-10 scale in a blinded fashion. Time to

complete epithelialization will be determined by the treating physician, and photo documentation will be submitted for blinded review by the independent surgeons. Any case of failed epithelialization that does not completely epithelialize within 90 days after surgery will be categorized as “greater than 90 days for analysis”, and all study-related patient contact will cease at that time.

16. Descriptive statistics will be reported. Univariate statistics will be used to compare primary and secondary outcomes between groups.

Premature Termination of Study:

This study may be prematurely terminated by the study team at any point if outcomes appear unequivocally worse than standard of care, if unusual types or rates of complications occur, or if any other safety concerns arise. An interim analysis will be performed in order to assess comparative outcomes following successful treatment of 20 subjects and determine whether to proceed with the remainder of the study.

Variables:

1. Surgical harvest technique will not be standardized between surgeons with the exception of requiring suprafascial harvest overlying the area to be grafted.
2. Donor site of split-thickness graft will be at surgeon discretion.

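### Time to complete epithelialization is set by the treating physician, who in effect knows the arm, and the blinded photo review has no stated effect on the recorded date

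*Protocol*

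**What the plan says.** Secondary Outcomes, item 4, covers patients with tendon exposure and defines healing time as "measured as time from surgery to first documentation of complete epithelialization in days". It does not say whose documentation counts.

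Item 15 of the Protocol section says who reads what:

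- **Readers.** Two surgeons with relevant expertise "who will not be involved in enrollment of patients in this trial or of management of their wounds".
- **Graft incorporation and tendon exposure.** "The percentage of graft incorporation and presence or absence of tendon exposure will be documented by each physician in a blinded fashion".
- **Appearance.** "The independent surgeons will also rate donor site graft aesthetic appearance on a 1-10 scale in a blinded fashion".
- **Healing time.** "complete epithelialization will be determined by the treating physician", and "photo documentation will be submitted for blinded review by the independent surgeons".

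Item 15 also puts wounds that have not closed by day 90 into a category of their own and ends study contact at that time. Item 14 continues photographs until the wound has closed and needs no more care, with timing and method tailored to the patient. Item 16 compares secondary outcomes between the arms.

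**The concern.** Whether a wound has fully closed is a judgement. For the other photo-read outcomes the protocol gives that judgement to readers outside the patient's care and blinded to arm. For this one it gives the recorded value to the physician treating the wound, and leaves the blinded reading without a consequence.

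Someone who knows the arm may call closure sooner in one arm than in the other, without intending to. That would shift the healing-time comparison and could decide whether a patient falls beyond day 90. The protocol describes the trial as a source of preliminary data, so a distorted healing-time signal could carry into the planning of a later study.

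**Working it through.** **1. The rules side by side.**

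| Outcome | Who sets the value | Role of the blinded surgeons |
|---|---|---|
| Tendon exposure | Independent surgeons | Set the value |
| Graft incorporation | Independent surgeons | Set the value |
| Appearance | Independent surgeons | Set the value |
| Time to epithelialization | Treating physician | Receive photographs; effect on the date not stated |

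The last row is a stated rule, because item 15 assigns the determination. What is unstated is whether the review confirms, replaces or overrides that determination, and how disagreement is settled.

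**2. Is the treating physician unblinded?** The protocol does not say so. The Randomization section has the arm assigned when surgery is scheduled. Item 6 describes placing the matrix under the graft, which happens in the intervention arm only. No blinding of the treating team is described. The inference is strong, but it is an inference.

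**3. Could the review correct an early call afterwards?** Under item 14 photographs stop once the wound is closed. If the treating physician's call ends the series, there may be no later photograph. The readers could then disagree with the date but could not supply a better one.

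**4. The plan's own figure.** Goal Enrollment gives 100 per arm for 25% against 10%, 80% power and alpha 0.05. Taking alpha as two-sided, with pooled variance and no continuity correction:

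- mean proportion = (0.25 + 0.10)/2 = 0.175
- n = [1.960 × √(2 × 0.175 × 0.825) + 0.842 × √(0.25 × 0.75 + 0.10 × 0.90)]² / 0.15² = 99.5, rounded up to 100

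The figure reproduces. The point does not depend on it, but the two rates give the expected counts below.

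**5. How many patients contribute.** Inputs from Goal Enrollment: 40 patients allocated 1:1, so 20 per arm; rates 25% and 10%.

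- Control: 20 × 0.25 = 5
- Restrata: 20 × 0.10 = 2
- Total: 7 of 40
- Chance of no contributing Restrata patient: 0.9²⁰ = 0.12
- Chance of at most one: 0.9²⁰ + 20 × 0.1 × 0.9¹⁹ = 0.12 + 0.27 = 0.39

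These are four-week rates. Secondary outcome 4 does not restrict exposure to week four, so patients exposed only at two weeks could add some.

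**6. What one shifted date does.** The protocol sets no photograph interval after four weeks. Assume, for illustration only, 7 to 14 days between looks. Calling closure one look early moves that patient's time by 7/90 = 8% to 14/90 = 16% of the 90-day window. If all contributing wounds close within 90 days, the mean of the arm moves by:

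- 2 patients (Restrata): 7/2 = 3.5 to 14/2 = 7 days
- 5 patients (control): 7/5 = 1.4 to 14/5 = 2.8 days

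This shows sensitivity to a single call. It does not estimate the probability or the direction of a miscall.

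**The case against.** The strongest reply is that the safeguard is in the same sentence: "photo documentation will be submitted for blinded review by the independent surgeons". Its natural purpose is to check the physician's determination, and the rule for settling differences could be left to an analysis plan or reading manual. This stands in part. A blinded look is planned, and a short clarification might be enough. But the protocol already assigns the determination to the treating physician, so a later document that gave the date to the readers would change the stated rule.

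Other objections limit the point:

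- A reader might infer that the treating physician also decides when the wound is looked at and so controls both timing and verdict. Item 14 does not support this. It says follow-up will be tailored without saying by whom, and lists patients, family, home health, the wound team and physicians as possible photographers.
- A reader might infer that blinded reading would remove the bias altogether. It would not. It addresses the judgement of closure, not when a photograph happens to be taken. Later photographs also have no stated quality standard, so the treating physician's direct examination has real value.
- Holding every case open until the readers confirm closure would need rolling reads, which the protocol does not describe.
- With about 5 against 2 patients the comparison is weakly informative whoever sets the date. That lowers the stakes but is no reason to keep the less protected assessment.

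**Conclusion.** The point holds for secondary outcome 4 and the category beyond day 90. The recorded value rests with a physician who almost certainly knows the arm, and the planned blinded review has no stated effect on it. With about 7 contributing patients expected, one or two shifted dates could change the comparison.

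This rests on the inference that the treating physician is unblinded and on the protocol's four-week rates; the size of a shift rests on an assumed interval between looks. The documents do not show that bias will occur or which arm it would favour. Nor does the point reach the primary outcomes, which are read blinded by two independent surgeons.

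Severity is low to moderate: one of six secondary outcomes, in a small subset, in a trial that the protocol itself says is not designed as a true test of its hypothesis.

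**What to change.** Amend item 15 and Secondary Outcomes item 4 as follows:

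1. The analysis date is the date of the first photograph that both blinded surgeons judge completely epithelialized. The category beyond day 90 follows the same reading.
2. State how reader disagreement is settled, for example by consensus of the two readers, and how a patient is handled whose photographs end without agreement.
3. Report the comparison using the treating physician's date as a sensitivity analysis.
4. Where practical, obtain one confirmatory photograph after the physician's call, no later than day 90, so that an early call can be corrected. This needs no rolling reads. Wound-care decisions stay with the treating physician.

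At the least, the protocol should state what the blinded review does to the recorded date.

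The cost is protocol wording and a few extra photographs; the readers and the photographic process are already planned, and sample size, power and alpha do not change. Two limits remain: later photographs may be taken by patients and vary in quality, and bias from individualized photograph timing is reduced but not removed.

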17. Utilization of purse string suture or other methods to narrow the flap donor site wound prior to grafting.
18. Decision to pursue secondary wound care strategy will be at surgeon discretion, including timing and type of treatment.

Funding Source and Funding Needs:

All Restrata products will be provided at no cost to patients by Acera Surgical Inc. No additional financial resources will be necessary to support this project.

Background Information:

Restrata (Acera Surgical, St. Louis, MO) is a synthetic hybrid-scale fiber matrix that possesses a fibrous structure of varying fiber diameters with high porosity [1]. The architecture of the material, which is similar to native extracellular matrix, allows for cell ingress and retention, as well as neovascularization of newly forming tissue, before completely degrading via hydrolysis [1]. The electrospun matrix is composed of two synthetic biocompatible polymers, polyglactin 910 (PLGA 10:90) and polydioxanone (PDO), both of which are used in other (FDA)-cleared devices, including dura substitutes, resorbable sutures, and orthopedic implants [1]. PLGA 10:90 and PDO were specifically selected in order to achieve a matrix with optimal handling properties and a rate of resorption ideally matched to the process of new tissue formation and wound healing. These polymers are co-electrospun into soft, white, compliant, non-woven sheets capable of supporting the natural wound healing process [1]. Once applied to a wound, the matrix supports cellular infiltration, new tissue formation, and wound healing while progressively resorbing into the tissue over the course of two weeks, on average.

Multiple clinical studies, including retrospective analyses, prospective analyses, and case reports have been conducted to evaluate the clinical efficacy of the synthetic hybrid-scale fiber matrix across multiple use cases in the wound care setting. A summary of the clinical studies and

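### Is it a defect that percentage graft incorporation is compared without adjusting for wound area?

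*Protocol*

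**What the plan says.** Step 16 of the Protocol announces descriptive statistics and then "Univariate statistics will be used to compare primary and secondary outcomes between groups". It names no particular test. The second primary outcome is "Percentage of surface area of split-thickness skin graft incorporation at four weeks post-operatively". The Covariates Recorded list includes "Wound surface area in square cm", without a time of measurement and without a role in the analysis. Goal Enrollment sets "40 total patients with 1:1 group enrollment" and admits that "this design is not truly hypothesis testing".

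Three further places bear on the covariate. Randomization "Occurs when the patient is scheduled for surgery", so the arm is fixed before there is a wound. The Variables list says "Surgical harvest technique will not be standardized between surgeons", apart from the requirement of a suprafascial harvest. It also lists, as something that may vary, "Utilization of purse string suture or other methods to narrow the flap donor site wound prior to grafting".

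**The concern.** A larger wound might take a graft less well. If so, wound area predicts incorporation, and a linear model with arm and area would estimate the treatment difference more precisely than a plain comparison. The randomisation is not stratified, so with 20 per arm wound size can differ noticeably between arms by chance, and an unadjusted estimate carries that imbalance. In a study whose useful product is an estimate with its interval, not a test, giving up precision on the only continuous primary outcome looks like an avoidable loss, since the covariate is to be collected anyway. At stake would be a wider interval, and a result that readers could attribute to unequal wounds.

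**Working it through.** **Inputs.** From the Protocol: N = 40, 20 per arm (Goal Enrollment); unadjusted comparison (step 16); area recorded (Covariates Recorded). Not in the Protocol, hence assumed: the correlation r between area and incorporation, taken from 0 to 0.5; no dropout. Results are in SD units.

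**1. The plan's own figure.** For 25% against 10%, two-sided 5%, 80% power, pooled variance: n = [1.960 × √(2 × 0.175 × 0.825) + 0.842 × √(0.25 × 0.75 + 0.10 × 0.90)]² / 0.15² = 99.5, so 100 per arm, as stated. It concerns tendon exposure and does not bear on this question.

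**2. Precision.** Adjusted over unadjusted variance = (1 − r²)(N − 3)/(N − 4) = (1 − r²) × 37/36.

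| r | variance ratio | equivalent N (40/ratio) | 95% interval |
|---|---|---|---|
| 0 | 1.028 | 38.9 | 1.5% wider |
| 0.2 | 0.987 | 40.5 | 0.6% narrower |
| 0.3 | 0.935 | 42.8 | 3% narrower |
| 0.4 | 0.863 | 46.3 | 7% narrower |
| 0.5 | 0.771 | 51.9 | 12% narrower |

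Break-even: (1 − r²) × 37/36 = 1 gives r = √(1/37) = 0.164. In simulations with outcomes capped at 100%, the gain shrinks: the ratio is 0.951 at nominal r = 0.3 and 0.825 at 0.5. The outcome is already a percentage of the grafted surface, so it is scaled to wound size and a strong correlation cannot be presumed.

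**3. Chance imbalance.** The difference in mean area has SD √(2/20) = 0.316, so it exceeds 0.5 SD with probability P(|Z| > 1.58) = 0.114. A 0.5 SD imbalance moves the unadjusted estimate by 0.5 × r: 0.15 SD at r = 0.3 and 0.25 SD at r = 0.5. Among only those 11% of trials, the simulated false-positive rate is 7.8% and 13.6%. Over all trials it is 4.9–5.1%: chance imbalance is already part of the standard error of the unadjusted comparison.

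**4. Dependence of area on the arm.** If area differs systematically between arms by s SD, adjustment introduces a bias of about r × s. The unadjusted variance is 2/20 = 0.100. The variance saved, and the shift that cancels it, are:

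- r = 0.3: 0.100 × (1 − 0.935) = 0.0065; √0.0065 = 0.081; s = 0.081/0.3 = 0.27.
- r = 0.5: 0.100 × (1 − 0.771) = 0.0229; √0.0229 = 0.151; s = 0.151/0.5 = 0.30.

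This ignores the small extra variance that a shift brings, which lowers both thresholds. In simulation, an illustrative shift of 0.5 SD gave the adjusted estimate a bias of 0.15 SD (r = 0.3) to 0.25 SD (r = 0.5) and a type I error of 7.6% to 13.7%. That is as large as the harm in step 3, but it would be present in every such trial, not in the one in nine with a large chance imbalance.

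**5. The comparator.** Because step 16 names no test, an unadjusted rank test fits it as well as a comparison of means. In simulations with a ceiling-bounded outcome, the rank test had more power than the one-covariate linear model for r up to 0.3 in one assumed outcome shape (0.595 against 0.570). In a more skewed shape it was ahead for r up to 0.2, the highest value completed there (0.674 against 0.526). The linear model was ahead only at r = 0.5. These figures depend on the assumed shapes and show only that the linear model is not uniformly better.

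**The case for a change.** The best case for adjustment is that the trade is lopsided. A useless covariate costs about one patient in 40, while r between 0.3 and 0.5 is worth about 3 to 12 more. At the Protocol's expected 35 × 0.70 = 24.5 enrolments a year, that is roughly 1.4 to 6 months of recruitment. The model-based test also holds about 5% when area is unrelated to the arm. The hazard in step 4 could be reduced by recording area at the end of harvest, before narrowing and before the matrix is applied. That timing has to be fixed in advance, because a later SAP cannot recover a measurement that was not taken.

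The arithmetic stands, and so does the observation that the Protocol does not say when area is measured. Three things limit the argument:

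- Its size rests on an r that no part of the Protocol supports.
- Measuring at the end of harvest is still after randomisation. The Protocol provides blinded photo review but nowhere says that the operating surgeon is unaware of the arm at harvest, and harvest technique is largely left to the surgeon. An earlier measurement closes the narrowing route only.
- Step 6 applies the matrix to the part of the wound bed that cannot be closed primarily. Area before narrowing is therefore not the grafted area, so the safer covariate may also be the weaker one.

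The unstated timing matters mainly if area enters a model, which the Protocol does not plan.

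**Conclusion.** The concern does not hold. Step 16 specifies a valid comparison that keeps its 5% level, and it contradicts nothing else in the Protocol. Adjustment for wound area would be an optional refinement of uncertain value: a slight loss for r below about 0.16, an interval about 3% narrower at r = 0.3, and about 12% narrower only at r = 0.5, with less gain where many patients reach full incorporation. Against this stands a covariate measured after randomisation, for which a systematic difference between arms of about 0.27 to 0.30 SD removes the benefit. Reasonable statisticians would choose differently here. Tendon exposure, the outcome of the hypothesis and the power analysis, is untouched either way. Step 16 does not rule out a supplementary adjusted model, and a SAP, if there is one, could add it. The conclusion rests on the assumed range of r, on no dropout, and on the Protocol's own description of the study as practically sized and preliminary.
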